# b) Reporting Procedures for Serious Adverse Events or Reactions

A serious adverse event (SAE) occurring to a participant should be reported to UoN FMHS UREC where, in the opinion of the PI, the event was 'related' (resulted from administration of any of the research procedures) and 'unexpected' (the type of event is not listed on this form as an expected occurrence). Reports of related and unexpected SAE's should be submitted by the PI within 7 days of the event. For fatal and life-threatening SUSARs, this will be done no later than 3 calendar days after the Sponsor or PI is first aware of the reaction. Any additional relevant information will be reported within 7 calendar days of the initial report.

# c) Safety of Participants

# What level of baseline screening will take place for this study?

- Self-reported medical history, including medication use will be taken.
- Self-reported regular moderate exercise.
- Participation screening questionnaire
- MRI screening questionnaire

## Provide details about the safety monitoring of participants and the staff/researchers carrying this out

When they are in the magnet, the participant will be given a button to push if they wish to speak with the operator, or if they wish to stop the scans at any point, and will be told to push the button if they feel uncomfortable, anxious or experience any unusual feelings such as heat, nausea, tremor or muscle twitches. MR scanner operators have undergone training in how to recognise, monitor and address side effects of MRS.

Participants will be observed when they stand up after being in the magnet for an extended period of time and they will be told to inform the researchers if they feel lightheaded at any point. In the event that an individual does feel faint, first aid measures will be implemented. When the symptoms resolve, gradual position changes from supine to upright will be carried out with participant feedback elicited at each stage to determine any return of symptoms.

Any adverse events that occur will be documented and filed in the participant's CRF and the event reported to the PI for review. Any serious adverse event will be documented and reported as described in section 7b.

#### Give details on the medical cover required and who will provide this cover

Study procedures do not require specific observation/monitoring by a medically-qualified professional. However, the PI (who is medically qualified) will be available by phone if researchers need support or advice, with nurses present for blood collection to assist and support researchers if required.

# Will the participants' GP be informed about their participation in the study?

The participants' GP will not be informed about their participation in the study. However, details of the volunteer's GP will be taken at screening and they will be informed if any incidental findings are discovered

## What is your planned procedure if an incidental finding is suspected?

If an incidental finding is discovered at screening or during brain imaging, initially this will be reported to the PI and the clinical significance of the finding assessed. Researchers will then inform the participant's GP if clinically significant and follow the wishes of the participant (sought at screening and documented on the SPMIC 'Abnormal Scans' form) regarding whether they wish for researchers to explain any findings to them directly, or for their GP to do this.

#### d) Ethical Considerations

Most research carries the risk of some ethical challenge. If this is the case you need to demonstrate your awareness of the problem and your response to mitigate ethical objections. There is a free text box below to detail any study specific ethical issues, however the following areas are often a cause for concern:

Will you include any vulnerable participants? (e.g. children (under 16 years old) or vulnerable adults with a mental incapacity or prisoners)  If yes, please describe how they are defined as vulnerable and detail any approved procedures or guidance that you feel apply.	Yes	No ✓	
Will taking part in the research put participants under any particular burden and/ or risk?  If yes, describe how this will be mitigated.	Yes 🔀	No	
The length of time that the participant is in the scanner will be up to 1hr, which may become uncomfortable. Care is taken when initially positioning the participant on the scanner bed that they are made as comfortable as possible and regular contact with the participant is maintained during the scanning period to check on their welfare. Scan sequences can be halted to allow repositioning and the participant will be removed from the scanner at any point that they need a break.			
Moderate exercise is not considered burdensome given health and exercise screening of participants.			
Will the research involve deliberate * deception * of participants?	Yes	No ✓	
If yes , justify why deception is used, describe deception and debriefing process, and include debriefing documents in the application.			

Will any procedures affect your own or any member of the research teams physical	Yes	No ✓
and/ or psychological safety as a researcher?		
If yes, describe how this will be mitigated.		
Does your research raise issues relevant to the Counter-Terrorism and Security Act (the	Yes	No ✓
Prevent Duty), which seeks to prevent people from being drawn into terrorism?		
If yes, please say how you plan to address any related risks.		
Please give details of any other study-specific ethical and/or safety considerations.		
Blood sampling carries usual risks associated with phlebotomy and extraction.		
In 2020 and early 2021 in vivo human research was severely impacted by the Covid pander		

# **Analysis of Outcome Measures**

# MAGNETIC RESONANCE IMAGES AND SPECTRA ANALYSIS

liver compared to muscle glycogen stores, and provide pilot data for future studies.

Participants will be scanned on a 3T Philips Achieva system using a 12cm Pulseteq surface coil. Natural Abundance 13C MRS will be performed with standard block pulses and data fitted using jMRUI and in-house fitting algorithms written in Matlab. Glycogen concentration will be determined using an external reference and

phantom replacement and values before and after exercise compared (1 - add). The liver glycogen scan takes ~15 minutes and the muscle glycogen scan takes ~10 minutes.

#### **BLOOD SAMPLE ANALYSIS**

Samples will be stored in a linked anonymised format and labelled using a combination of study reference, unique study identifier and cross referenced with location code numbers to permit accurate linkage to study data and the consent form. The master database will be held by the study investigators in a password encrypted file.

Blood samples will be processed in the Nottingham Digestive Diseases Centre (NDDC) laboratories, University of Nottingham (located in the QMC) or SPMIC laboratories (on University Park Campus). Samples will be transported from SPMIC following local standard operating procedures and stored securely in the NDDC laboratories at -80°C prior to analysis. The analysis of samples will take place either in the NDDC laboratories, University of Nottingham or else samples will be shipped to commercial providers for specialist analyses with a material transfer agreement arranged.

Once the study is completed and analysis has taken place, any residual samples will be stored within the Nottingham Digestive Diseases Centre Biomedical Research Unit Research Tissue Bank for future research (DI [name]- Licence Number 12265) if participants are agreeable and sign the optional clause on the consent form. Where participants do not agree to the future use of the samples, they will be destroyed in accordance with the Human Tissue Act, 2004.

Standard operating procedures (SOPs) will be followed for all laboratory assays to ensure the high quality and reliability of our generated data.

## **STATISTICS**

Statistical analyses will be conducted by [name], with the supervision and support of [name] and [name]. Data input, cleaning and analysis will be conducted using SPSS. Initially, an ANOVA f-test will be applied to the data comparing pre and post exercise values for each week of the menstrual cycle and any significant mains effect or interaction between exercise and week will be followed up by a means difference t-test. Change in glycogen during each week will also be analysed using a means difference t-test with significant changes ( $p \le 0.05$ ) reported.

Baseline characteristics of participants, outcome measures at baseline (liver fat content, blood biomarkers) and each period time-point will be summarized using descriptive statistics. Data will be presented as mean $\pm$  standard deviation and the significance of difference will be set at p <0.05. Any changes in the planned statistical methods will be documented in the trial report.

All data will be anonymised and analyses will be conducted on UoN computers/laptops or at Nippon Sports Science University. Uon data are regularly backed up to UoN servers and data will be stored for up to 7 years before being deleted.

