#### 3. BACKGROUND AND RATIONALE

## **Background**

In recent years, the activities of female athletes have been increasing. However, the blood concentrations of female hormones change significantly for premenopausal women throughout the menstrual cycle (1). Therefore, since the condition of the body changes with the menstrual cycle, it is necessary to establish a conditioning method that considers the menstrual cycle.

Previous work undertaken by co-investigator at Nippon Sports University (Tokyo) has shown that oxidative stress and serum carnitine, which are physiological indices highly related to fatigue, differ through the menstrual cycle (2,3). In addition, studies suggest that the menstrual cycle influences muscle glycogen utilization during high-intensity intermittent exercise until exhaustion in women with habitual exercise activity (European Journal of Sport Science, under revision). Estrogen promotes increased fat oxidation, sparing muscle and hepatic glycogen, decreasing gluconeogenesis, and increasing the exercise time until exhaustion (4). Progesterone is known to reverse several estrogenic effects, including reducing fat oxidation (5). The amount of glycogen stored in the body, either in liver or muscle, is highly related to fatigue and exercise performance. However, the study of a 30-kg box lifting and transport exercise is the only study of the menstrual cycle and liver glycogen by human (6). Furthermore, the study has compared in the early follicular phases (E-FP) when both of serum estradiol and progesterone concentrations are low with in the luteal phase (LP) when both of serum estrogen and progesterone concentrations are high; however, the LP is characterized by high estradiol and progesterone concentrations, and it is thus not possible to determine the effects of estradiol alone. Therefore, conducting measurements in the late follicular phase (L-FP), when serum estradiol concentrations are high but serum progesterone concentrations are low, is necessary to confirm the effects of estrogen alone.

**Aim:** To investigate the effects of hormonal changes throughout the menstrual cycle on moderate exercise induced liver and muscle glycogen changes in healthy women.

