#### 4. PARTICIPANTS

## **Description of study participants**

12 healthy females aged 18-35 with regular menstrual cycle (every 25 - 38 days), who take regular exercise. Participants must have no use of any oral contraceptives or other hormone medications for at least 6 months prior to the experiment.

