#### 5. STUDY PROCEDURES

## **Study Visits**

The participants will be required to visit the research centre on 5 separate occasions, first for a preliminary setup visit and subsequently at 4 points during the menstrual cycle. Each participant will be assigned a trial identity code number for use on trial documents, samples and the electronic database enabling anonymous linkage of the bio-samples and data collected. At visits 2-5, a blood sample of up to 20ml will be collected by a researcher trained in venepuncture. During exercise visits, participants will be supervised by a researcher trained in basic life support and a qualified first aider will be present in the SPMIC in case participant feels faint or needs to immediately stop for any reason.

[figure not shown]
Participants will instructed to refrain from strenuous exercise on the day before visits, to maintain their normal diets, and to keep a diet diary for 2 days prior to each trial. All Participants consume the same standardized dinner on the evening before each test day, which will consist of a frozen tomato pasta vegetarian ready meal provided by the researchers.

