#### **Expenses and benefits**

This study requires participants to attend 5 visits in total, 1 initial visit and 4 weekly study visits. Each visit will last a full morning, requiring blood sampling and moderate exercise for one hour. An appropriate inconvenience allowance for this commitment of £75 per visit will be offered, and a further £25 on completion of the study, equalling a total of £400.

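### The analysis compares weeks of the cycle, but the study asks about hormonal phases; weeks 2 and 3 mix phases across women, and the late follicular contrast is not tested

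*Protocol*

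**What the plan says.** The Background (section 3) names three hormonal states: E-FP (both hormones low), L-FP (estradiol high, progesterone low) and LP (both high). It faults earlier work for comparing only E-FP with LP, and says that "conducting measurements in the late follicular phase (L-FP), when serum estradiol concentrations are high but serum progesterone concentrations are low, is necessary" to show what estrogen does alone.

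The population is "12 healthy females aged 18-35 with regular menstrual cycle (every 25 - 38 days" (section 4, Description of study participants).

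Visit timing is described in two ways. Study Visits (section 5) places the visits, after the set-up visit, "subsequently at 4 points during the menstrual cycle". Expenses and benefits says "1 initial visit and 4 weekly study visits", and the intervention table in section 6 also gives four weekly visits.

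The Statistics text (section 8) uses week throughout. The "ANOVA f-test will be applied to the data comparing pre and post exercise values for each week of the menstrual cycle", a significant main effect or "interaction between exercise and week will be followed up by a means difference t-test", and "Change in glycogen during each week will also be analysed using a means difference t-test". On the threshold, "the significance of difference will be set at p <0.05". Phase does not appear in the analysis.

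Estradiol and progesterone are secondary endpoints (Synopsis), and blood is taken at visits 2 to 5. The stated use of the hormones is to relate them to glycogen, not to assign a visit to a phase.

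**The concern.** Week number stands in for phase only if women ovulate at about the same cycle day. With a 13-day range of eligible cycle lengths they need not, so one week number can be luteal in one woman and follicular in another. Averaging over them shrinks any phase difference and adds between-woman variance. Three named phases also do not map onto four weeks, so the protocol does not say which week is meant to be L-FP. At stake is the estrogen-alone contrast, which is the reason the Background gives for going beyond E-FP versus LP.

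**Working it through.** **Inputs from the protocol.** Cycle length 25 to 38 days; four visits 7 days apart; n = 12; alpha 0.05 (taken as two-sided). The sample size text in section 8 gives muscle glycogen depletion of 46.4 ± 8.4% (follicular) and 21.2 ± 16.3% (luteal), with ± read as a standard deviation. It gives no liver figures and no power target, so there is no stated power to reproduce.

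**Assumptions (not in the protocol).** First study visit on cycle day 3, so visits on days 3, 10, 17 and 24; the 14 whole-day cycle lengths equally likely; luteal length 14 days (range 12 to 16); within-woman correlation 0 or 0.5; every non-luteal visit given the follicular mean.

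**Starting point without mixing.** Difference = 46.4 − 21.2 = 25.2 points. SD of the paired difference at correlation 0 = √(8.4² + 16.3²) = 18.34; at 0.5 it is 14.12. Paired t-test power at n = 12 is 99% and above 99.9%.

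**Spread of ovulation.** Ovulation day = cycle length − 14: day 11 in a 25-day cycle, day 24 in a 38-day cycle. Visits spanning 21 days cover 21/25 = 84% of the shortest cycle and 21/38 = 55% of the longest.

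**Phase at each visit (14-day luteal phase).** A woman is past ovulation when visit day > cycle length − 14.

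| Week (day) | Past ovulation | L-FP, 4-day window | L-FP, 5-day window |
|---|---|---|---|
| 1 (3) | 0/14 | 0/14 | 0/14 |
| 2 (10) | 0/14 | 3/14 = 21% | 4/14 = 29% |
| 3 (17) | 6/14 = 43% | 4/14 = 29% | 5/14 = 36% |
| 4 (24) | 13/14 = 93% | 1/14 = 7% | 1/14 = 7% |

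Both windows end on ovulation day. No week has an L-FP majority. With the four-day window, cycles of 28, 29, 30, 35, 36 and 37 days have no L-FP visit: 6/14 = 43%. With the five-day window, cycles of 29, 30, 36 and 37 days have none: 4/14 = 29%.

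For luteal lengths of 12 and 16 days, the share past ovulation is 4/14 = 29% and 8/14 = 57% at week 3, and 11/14 = 79% and 14/14 = 100% at week 4.

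**Effect on the comparisons.** Diluted difference = 25.2 × share past ovulation. Power is by simulation of a paired t-test at n = 12; each pair is for correlation 0 and 0.5.

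| Comparison | Luteal length | Difference (points) | Power |
|---|---|---|---|
| Week 1 vs 3 | 12 | 25.2 × 4/14 = 7.2 | 20%, 25% |
| Week 1 vs 3 | 14 | 25.2 × 6/14 = 10.8 | 39%, 51% |
| Week 1 vs 3 | 16 | 25.2 × 8/14 = 14.4 | 62%, 76% |
| Week 1 vs 4 | 12 | 25.2 × 11/14 = 19.8 | 88%, 97% |
| Week 1 vs 4 | 14 | 25.2 × 13/14 = 23.4 | 97%, above 99% |

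**Sensitivity to the first visit day (14-day luteal phase).** If the first study visit falls anywhere on days 1 to 7, week 3 is 50% luteal, 28% L-FP and 21% mid-follicular, and 57% of women have any L-FP visit (four-day window). If visits have no anchor to menses, every week has about the same mixture: 16% E-FP, 26% mid-follicular, 13% L-FP and 45% luteal.

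**The case against.** The factor is week of the menstrual cycle, not calendar week, and the visits are placed at points in the cycle, so some anchor to menses is implied. With one, not every week mixes phases: on the assumptions above, week 1 is wholly follicular and week 4 is 79% to 100% luteal. The only numerical basis for n = 12 and the stated hypothesis both concern follicular versus luteal, and that contrast is nearly intact. This stands, and it limits the point.

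A reader might infer that the phase question cannot be answered at all, or that a null result would be uninterpretable. The protocol does not support either. Hormones are measured at each study visit, so visits could be classified, and a secondary objective relates hormones to glycogen whatever the week label.

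The even spread of cycle lengths is also an assumption, and it drives the week 3 loss. If lengths instead centred on 29 days (SD 2.5, also assumed), week 3 would be about 73% luteal and power about 82% to 93%. That helps the luteal comparison but not L-FP coverage: under a day 3 start and a four-day window, 28-, 29- and 30-day cycles are all among those missed.

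Finally, a figure in Study Visits is not shown and may give a schedule, and a separate statistical plan may exist. Neither would alter the fact that the protocol itself names week as the factor and sets weekly visits. This is also a 12-woman pilot with descriptive endpoints, which limits the consequences but does not make week the right factor.

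**Conclusion.** The point holds in this form: the analysis as written does not match the phase question. Weeks 2 and 3 mix phases, no week represents L-FP, and the estrogen-alone contrast is not among the planned comparisons.

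On the stated assumptions, week 1 versus week 3 keeps about 10.8 of 25.2 points (7.2 to 14.4 across luteal lengths), with power of about 39% to 51% (20% to 76%). Between 29% and 43% of women have no L-FP visit, depending on the window. The follicular versus luteal comparison through week 4 largely survives if visits are anchored to menses.

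The figures rest on the assumed first visit day, cycle-length distribution, luteal length and window width, and on muscle rather than liver data. Statements about visit anchoring apply to the visible text only. The mismatch between week and phase does not depend on any of these figures.

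**What to change.** - Replace week with phase as the repeated-measures factor. Assign each visit to E-FP, L-FP or LP from the date of menses onset and the estradiol and progesterone already assayed at that visit, with cut-offs fixed before glycogen values are seen.
- Name L-FP minus E-FP and LP minus E-FP as the contrasts for the exercise-induced change in liver glycogen. A mixed model with participant as a random effect would handle uneven numbers of visits per phase, but is optional.
- Time the visits to cycle phase rather than at fixed 7-day intervals. Relabelling visits afterwards cannot recover a woman who has no L-FP visit.
- Reconcile the four weekly visits with the four points in the cycle, and say which of the three named phases the fourth visit represents.

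The cost is protocol wording, analysis code and some flexibility in scheduling. The hormone assays are already planned. Phases will be slightly unbalanced across women, and visits will not be exactly 7 days apart.

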# 9. DATA MANAGEMENT

It is now a University governance requirement that every research project has a **Data Management Plan** (**DMP**): Here is the link to the required training course that will take 2-3 hours: DMP training

When you have completed the training a DMP is easy to create using DMPOnline at the following link: https://dmponline.dcc.ac.uk/ It is worth selecting the option for a research librarian if you have not completed the training. This should be appended to the end of this form.

# **Summary for Form**

Who will have access to the research data?	Direct access will be granted to authorised representatives from the University of Nottingham and any host institution for monitoring and/or audit of the study to ensure compliance with regulations.
How will research data be stored?	Blinded data will be stored on a computer at the SPMIC and in Nippon sports university.
How long will research data be stored for?	Research databases and records will be retained for 7 years after the end of the study. Consent will be obtained from participants at screening to retain their fully anonymised (not linked) MR images for future research use.
What will be done with the research data at the end of the storage period?	At the end of the storage period, all paper records will be securely destroyed through the University 'confidential waste' stream. Electronically held records and data will be erased, but anonymised images may be retained, in the SPMIC archive beyond the 7-year time frame, for future research use if consent was obtained from participants to do so.
Who will have access to the participants' personal data?	Only members of the research team who need the information to conduct study activity will have access to the participants' personal data. Access will be prior approved by the PI and documented in the Delegation log.
How will personal data be stored?	Personal, identifiable data will be held securely in a locked cabinet separately to anonymised study data
How long will personal data be stored for?	To comply with the data protection act, personal data will be deleted as soon as possible after it is no longer needed for the study. Personal details e.g. those contained in the screening questionnaires and consent forms will be retained until the data have been analysed and interpreted. They will then be securely destroyed  If the participant wishes to be informed of the results of the study, their contact details will be retained, and specific consent will be collected on the consent form.
Describe method(s) of research data	All study data will be entered on an Excel spreadsheet. The
entry/management	participants will be identified by a unique study specific number and/or code in any database. Their name or any other identifying detail will NOT be included in any study data electronic file. Any documentation with identifiable (personal) data will be stored securely and separate from the research data.

